3.4 Endpoints

- **Primary Endpoints:** The primary endpoints are the microbial counts for each product at baseline and 10 minutes post-application time point for both the abdomen and groin. \log_{10} CFU/cm² calculated based on the microbial counts will be used for primary analysis.
- **Secondary Endpoints:** The secondary endpoints are safety data including evaluations for skin reactions using the modified Berger Bowman irritation assessment scale and the incidence of adverse events reported during the study for all randomized subjects (the full Intent-to-Treat data set). Post treatment skin irritation scores of 3 on those scales are also considered adverse events.
- **Exploratory Endpoints:** The exploratory endpoints are \log_{10} CFU/cm² reductions from baseline for each treatment per body site per post-application time point.

- **Informational Endpoints:** The informational endpoints are product expression volumes. The weight of the treatment applied to a test site will be estimated by subtracting the weight measurement (g) of the treatment after the application from the weight of the treatment (g) before application.

3.5 Acceptance Criteria

The following table summarizes the minimum baseline criteria for each of the test sites and the expected minimum efficacy standards (superiority criteria).

Table 2: Minimum Treatment Baseline and Expected Mean Log₁₀ Reduction per Anatomical Site

Anatomical Site	Treatment Day Baseline Criteria	Expected Efficacy Standards
Abdomen	3.00 to 5.50 log ₁₀ CFU/cm ²	At 10 minutes, the lower two-sided 95% confidence bound of the average treatment effect of IP vs. VC and IP vs. SC should be greater than 1.2 log ₁₀
Groin	5.00 to 7.50 log ₁₀ CFU/cm ²	At 10 minutes, the lower two-sided 95% confidence bound of the average treatment effect of IP vs. VC and IP vs. SC should be greater than 1.2 log ₁₀

4 Sample Size

This is a phase 2 study to assess the immediate antimicrobial effect of the Investigational Products relative to the two negative controls using a log reduction study according to the procedures outlined in the Food and Drug Administration Tentative Final Monograph (TFM) for *Effectiveness Testing of a Patient Preoperative Skin Preparation* (FR 59:116, 17 June 94, pp. 31450-31452) and the test criteria outlined in the deferral letters from the FDA published on January 19, 2017. The purpose is to inform design of future efficacy studies. Therefore, no sample size calculation was performed to provide statistically-powered evidence of efficacy as part of this study. The sample size is deemed adequate for these purposes.

5 Intended Statistical Software

R 3.2.0 (2015-04-16) or later version if updated.

6 Data

6.1 Data Sets Analyzed

Descriptions of the modified intent to treat (mITT) data, per-protocol data and intent to treat (ITT) data are shown below. Inclusion for the per-protocol data / mITT data set is evaluated for each body area (left and right for the groin and abdomen).

- Modified Intent to Treat (mITT) data: data collected will be included if the treatment-day baseline counts are within the acceptable range ($\geq 3.00 - \leq 5.50 \log_{10} \text{ CFU/cm}^2$ on abdominal area, and $\geq 5.00 - \leq 7.50 \log_{10} \text{ CFU/cm}^2$ on inguinal area). Data collected will be excluded from mITT data if the treatment-day baseline counts are outside the acceptable range.
- Per-Protocol data: data collected will be included if the treatment-day baseline counts are within the acceptable range ($\geq 3.00 - \leq 5.50 \log_{10} \text{ CFU/cm}^2$ on abdominal area, and $\geq 5.00 - \leq 7.50 \log_{10} \text{ CFU/cm}^2$ on inguinal area). Data collected will be excluded from per-protocol data if the treatment-day baseline counts are outside the acceptable range.
- Intent to Treat (ITT) data: all randomized subjects with available data will be included and used for the ITT analysis. The full intent to treat (ITT) data set (all randomized subjects) will be used for the secondary analysis.

For $\log_{10} \text{ CFU/cm}^2$ determinations, missing data will not be imputed for either mITT data or Per Protocol data and will be excluded from analysis. For data points excluded from per-protocol analysis due to protocol deviations, those data points may be included in mITT analysis.

For primary analysis (average treatment effect correcting for pre-treatment \log_{10} bacterial counts) and exploratory analysis (log reduction), efficacy analyses will be first made on the modified intent to treat (mITT) data set. Efficacy analyses will be also conducted on the per-protocol data set as supportive analyses when per-protocol data are different from mITT data.

For informational analysis (product expression volumes), inclusion of data points will be based on whether the matching data point is included for efficacy for primary analysis. Analysis will be performed based on the per-protocol data as supportive analyses when per-protocol data are different from mITT data for product expression volumes.

6.2 Analysis Population Set(s)

For each treatment per body site, the number of subjects randomized with treatments received, the number of subjects available for mITT analysis and / or for per-protocol analysis at 10 minutes post-treatment time point will be provided in tables below (cf. Table 3, Table 4 and Table 5).

Table 3: Number of Subjects Randomized with Treatment Received

Treatment	Body Site	N Subjects Randomized with Treatment Received
A	Abdomen	
B	Abdomen	
C	Abdomen	
A	Groin	
B	Groin	
C	Groin	

Table 4: Number of subjects available for mITT analysis

Treatment	Body Site	N Subjects for mITT Treatment Effect	N Subjects for mITT log ₁₀ CFU Reduction	N Subjects for mITT Product Expression Volumes
A	Abdomen			
B	Abdomen			
C	Abdomen			
A	Groin			
B	Groin			
C	Groin			

Table 5: Number of subjects available for Per-protocol analysis

Treatment	Body Site	N Subjects for Per-protocol Treatment Effect	N Subjects for Per-protocol log ₁₀ CFU Reduction	N Subjects for Per-protocol Product Expression Volumes
A	Abdomen			
B	Abdomen			
C	Abdomen			
A	Groin			
B	Groin			
C	Groin			

7 Statistical Analysis/Calculations

7.1 Derived Variables

7.1.1 Log CFU/cm² of skin

The estimated log₁₀ number of viable microorganisms per cm² recovered from each sample site will be designated the “R-value”. To convert the volumetric measure of the sample into the number of colony-forming units per square centimeter (cm²), the following formula will be employed:

$$R = \log_{10} \left[\frac{F \left(\frac{\sum_{i=1}^n C_i}{n} \right) 10^{-D}}{A} \right] \quad (1)$$

Where:

R = the average colony-forming unit count in log₁₀ scale per cm² of sampling surface

F = Total number of mL of sampling solution (SS) added to the sampling cylinder (in this study, F = 6 mL for all samples)

$\frac{\sum_{i=1}^n C_i}{n}$ = average of the duplicate colony counts used for each sample collected (n = 2)

D = Dilution factor of the plates counted

A = Inside area of the sampling cylinder (A= 3.46 cm² in this study)

Note: The reason that a log₁₀ transformation will be performed on the collected data is to obtain a linear scale. A linear scale, more appropriately a log₁₀ linear scale, is a basic requirement of the statistical models used in this study.

If colonies on one of the plates are uncountable, the count from the remaining plate will be used.

In order to avoid potential calculation problems due to taking the logarithm of zero, counts of less than 1 CFU/cm² are treated as 1 CFU/cm², such that the log₁₀ transformation is no less than zero.

7.1.2 Log Reduction

Log₁₀ CFU/cm² reductions from baseline will be calculated separately for each subject, each post-application time point, and each of the treated anatomical sites by taking the baseline log₁₀ CFU/cm² values and then subtracting the log₁₀ CFU/cm² values for the samples taken after the baseline.

7.1.3 Product Expression Volumes

The weight of drug product applied to a test site will be estimated by subtracting the weight measurement of the test material after the application from the weight of the test material before application.

7.2 Handling of Missing Data

For log₁₀ CFU/cm² determinations, missing data will not be imputed for either mITT data or Per Protocol data and will be excluded from analysis.

7.3 Summary Statistics

Summary statistics will be provided for \log_{10} CFU/cm² of skin, \log_{10} CFU/cm² reduction and product expression volumes based on mITT data and/or per-protocol data. For continuous variables, data will be summarized with the following descriptive statistics: number of observations, mean (LSMean), median, standard deviation and range (minimum - maximum). See examples for summary statistics Tables 6 and 7 below for \log_{10} CFU/cm² and \log_{10} CFU/cm² reduction.

Table 6: Example: summary statistics for \log_{10} CFU/cm² for Groin

\log_{10} CFU/cm ²	Treatment	Time Point	N	Mean	LSMean	Median	SD	Range
\log_{10} CFU/cm ²	A	Baseline	24	5.92	5.92	5.82	0.53	5.01 - 7.23
\log_{10} CFU/cm ²	A	10 Minutes	24	3.29	3.29	3.44	1.10	0.89 - 5.89
\log_{10} CFU/cm ²	B	Baseline	24	5.78	5.78	5.66	0.54	5.05 - 7.04
\log_{10} CFU/cm ²	B	10 Minutes	24	3.27	3.27	3.43	1.09	0.00 - 4.95
\log_{10} CFU/cm ²	C	Baseline	24	5.92	5.92	5.82	0.53	5.01 - 7.23
\log_{10} CFU/cm ²	C	10 Minutes	24	3.05	3.05	3.09	0.72	1.22 - 4.09

Table 7: Example: summary statistics for \log_{10} CFU/cm² reduction for Groin

\log_{10} CFU/cm ² reduction	Treatment	N	Mean	LSMean	Median	SD	Range
\log_{10} CFU/cm ² reduction	A Baseline - 10 Minutes	24	2.63	2.63	2.57	1.18	0.20 - 4.80
\log_{10} CFU/cm ² reduction	B Baseline - 10 Minutes	24	2.83	2.83	2.83	0.89	1.24 - 4.86
\log_{10} CFU/cm ² reduction	C Baseline - 10 Minutes	24	2.52	2.52	2.33	1.09	0.83 - 5.50

7.4 Analysis Methods

For each body site, when per-protocol data are different from mITT data for \log_{10} CFU/cm², log reduction, or product expression volumes, per-protocol analysis and mITT analysis will be performed separately using the same statistical methods. The following analysis methods will be applied to both per-protocol analysis and mITT analysis, both abdomen and groin.

An alpha level of 5% (two-sided) is used for all analyses.

7.4.1 Primary Analysis

An analysis of variance (ANOVA) of the baseline \log_{10} CFU/cm² values will be performed separately for abdomen and groin. In each model, there will be a random subject effect, a fixed treatment effect, a fixed body side effect and the interaction between treatment and body side. Pairwise comparisons with Tukey's method will be made for \log_{10} CFU/cm² to determine if there is any significant difference between treatments at baseline after adjusting body side (e.g., randomization has produced treatment arms with similar baseline CFU values) for each body site.

The primary purpose of the study is to compare the immediate antimicrobial activity of the Investigational Products to the Negative Control according to the methods described in the FDA TFM with the statistical analyses outlined in a deferral letter published January 19, 2017 for superiority.

Evaluate the treatment effect at 10 minutes for Investigational Product (IP) vs. Vehicle Control (VC) / Saline Control (SC) for abdomen and groin by comparing to a superiority margin of 1.2 \log_{10} .

- Ho: treatment effect of IP vs. VC/SC correcting for pre-treatment \log_{10} bacterial counts $\leq 1.2 \log_{10}$
- Ha: treatment effect of IP vs. VC/SC correcting for pre-treatment \log_{10} bacterial counts $> 1.2 \log_{10}$

Ho is the null hypothesis and Ha is the alternative hypothesis.

A linear regression model for each body site will be used for primary analyses. In the model, the response is the post-treatment \log_{10} bacterial counts and predictors are the treatment effect as a fixed effect and the pre-treatment \log_{10} bacterial counts as a covariate. The two-way interaction between the treatment and pre-treatment \log_{10} bacterial counts will also be explored. If there is no significant interaction detected, the interaction term will be removed from the model and the average difference between treatments correcting for pre-treatment bacterial loads will be estimated from the linear regression model. If there is a significant interaction detected between treatment and pre-treatment \log_{10} bacterial counts, the average difference between treatments will be estimated from the linear regression model at the average of the covariate.

The average treatment effect along with 95% confidence interval between IP and VC/SC will be estimated from the model above for each body site and compared to a superiority margin of 1.2. If the two-sided 95% lower confidence bound $> 1.2 \log_{10}$, the null hypothesis for superiority is rejected and it is concluded that IP is superior to VC/SC by passing the superiority margin of $1.2 \log_{10}$. Otherwise the superiority criteria cannot be passed.

The primary analysis will be based on the modified Intent to Treat (mITT) data set and the supportive analysis may be conducted using the per-protocol data set, as described in Section 6.

Since the study will declare success when and only when superiority is demonstrated for both IP vs. VC and IP vs. SC for both abdomen and groin, no multiplicity adjustment for multiple primary objectives is required^[1].

An example for results of comparisons above can be found in Table 8. All results that do not meet the targets are highlighted.

Table 8: Example: results for for IP vs. VC and SC for Groin

Comparison	N Pairs	Average Treatment Effect	Conf Int	Meet Superiority Criteria
IP vs. VC	24	1.23	0.90, 1.50	No
IP vs. SC	24	1.65	1.31, 1.99	Yes

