7.4.1.1 Treatment Balance

Each subject will receive two of the three possible treatments, one on the right side of the body and one on the left. A minimum of 36 evaluable subjects will be required to achieve a total of at least 24 test sites for groin and abdominal regions for each treatment.

The treatment assignments will be balanced such that the number of readings per anatomical site matches the calculated requirements.

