8.0 STUDY POPULATION

Healthy male and female volunteers, 18 years of age or older, with no dermatological conditions or known history of sensitivity to natural rubber latex, adhesive skin products (e.g., Band-Aids, medical tapes), polyester, Octenidine Dihydrochloride, or common personal care or beauty products will be enrolled into this study. A sufficient number of volunteers will be enrolled, such that a minimum total of 24 readings for the groin (sebaceous rich) region and 24 readings for the abdominal (sebaceous poor) region are evaluable for the Investigation Product (test article) and Negative Control arms; a minimum total of 24 readings for the groin region and 24 readings for the abdominal region are evaluable for the Vehicle Control arm and a minimum total of 24 readings for the groin region and 24 readings for the abdominal region are evaluable for the Saline Control arm

Subjects must satisfy all Treatment Day Inclusion/Exclusion Criteria prior to Treatment Day procedures. Subjects may qualify on the abdominal and/or inguinal sites and be admitted into testing for one or both anatomical sites, although if more subjects qualify for treatment than can be treated in a given time period, preferential admittance into the treatment phase will be given to subjects qualifying in both the

abdominal and inguinal test areas. To be included in the primary analysis (mITT data set), a treatment site must have a Treatment Day microbial baseline equal to or greater than the stated minimum requirement. Enrollment will continue until minimum number of subjects meeting baseline criteria on each body region per treatment arm is identified.

A minimum of 36 human subjects will be treated utilizing bilateral applications to ensure that the treatments will be evaluated on the sites as described in the following table. Each subject has four independent sampling sites: left and right sides for the abdomen and left and right sides for the groin.

Table 4.0: Estimated No. of readings per anatomical site (abdomen and groin), per treatment, per sampling interval (10-minutes)			
Arm	Treatment	Number of Abdomen Evaluations	Number of Groin Evaluations
Test article	Thermally treated polyester cloth impregnated with 0.4% w/v octenidine dihydrochloride	24	24
Vehicle Control	Thermally treated polyester cloth impregnated with vehicle formulation	24	24
Saline control	0.9% normal saline applied with polyester cloth	24	24

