17.3 Statistical Methods

17.3.1 Primary Analysis

An analysis of variance (ANOVA) of the baseline \log_{10} CFU/ cm^2 values will be performed separately for abdomen and groin to determine whether the randomization produced treatment arms with similar baseline CFU/ cm^2 values.

The primary purpose of the study is to compare the immediate antimicrobial activity of the Investigational Products to two negative controls according to the methods described in the FDA TFM using the statistical analyses outlined in the deferral letters published by the FDA on January 19, 2017.

Statistical hypotheses are:

Ho: Treatment effect of the Investigational Product vs. Vehicle Control / Saline Control ≤ 1.2

Ha: Treatment effect of the Investigational Product vs. Vehicle Control / Saline Control > 1.2

Ho: is the null hypothesis and Ha is the alternative hypothesis.

A linear regression model will be used for primary analysis. In the model, the response is the post-treatment \log_{10} bacterial counts and predictors are the treatment effect and the pre-treatment \log_{10} bacterial counts as a covariate. The interaction between the treatment and pre-treatment \log_{10} bacterial counts will be also explored. If there is no significant interaction detected between treatment and pre-treatment \log_{10} bacterial counts, the interaction term will be removed from the model and the average difference between treatments will be estimated from the linear regression model after correcting for pre-treatment \log_{10} bacterial counts. If there is a significant interaction detected between treatment and pre-treatment \log_{10} bacterial counts, the average difference between treatments will be estimated from the linear regression model after averaging over the interaction term. The objective is to achieve a difference

in treatment effect (\log_{10} reduction) for investigational products vs. negative controls greater than 1.2 \log_{10} on both the abdomen and groin with 95% confidence. The 95% confidence intervals will be summarized for each product tested, grouped by anatomical site and the 10 minute post-application time point and compared to the superiority margin of 1.2 \log_{10} for investigational products vs. each Negative Control.

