3.3 Study Design

This single site study is a randomized, blinded design employing a minimum of 36 healthy volunteers, where each subject receives two of the planned treatments on the abdomen and groin.

Treatment materials for the following treatment groups will be blinded with treatment codes A or B:

- Thermally treated cloth impregnated with 0.4% w/v octenidine dihydrochloride aqueous solution (IP: Investigational Product).

- Thermally treated cloth impregnated with vehicle formulation (VC: Vehicle Control).

The 0.9% Saline Control (SC) cannot be blinded due to product application requirements and will be assigned to treatment code C.

Out of the minimum 36 evaluable subjects, 12 subjects will receive treatments from both A and B, 12 subjects will receive treatments from both A and C, and 12 subjects will receive treatments from both B and C to achieve 24 test sites from A, B and C for groin and abdominal regions. The application will be randomized so that each treatment is applied on an equal number of left and right sides of the body. Due to baseline requirements the final data set may be imbalanced with regard to right and left sides upon achieving the minimum number of qualifying body sites.

Subjects will be sampled for treatment day baseline microbial populations on randomly assigned sites of the abdominal and inguinal areas on both sides. Subjects will have samples collected at baseline and 10 minutes (± 30 seconds) on both abdomen and inguinal sites. All sampling times will be calculated from the completion of the dry time of each product following application.

There is a neutralization test before the main treatment study. Note: this statistical analysis plan is only for the Main Treatment study and does not include the analysis for the Neutralization study. The analysis for the Neutralization study will be conducted by the clinical site and included in the final clinical report.

The group treatments and number of treatment sites planned for each group for the main treatment study are shown in Table 1.

Table 1: Group treatments and number of treatment sites planned

Arm	Treatment	Number of evaluable treatment sites per anatomical site
Investigational Product (IP)	Thermally treated polyester cloth impregnated with 0.4% w/v octenidine dihydrochloride	24
Vehicle Control (VC)	Thermally treated polyester cloth impregnated with vehicle formulation	24
Saline Control (SC)	0.9% normal saline applied with polyester cloth	24

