7.4.3 Exploratory Analyses

7.4.3.1 Log Reduction

Log₁₀ reductions will be compared between test materials by an Analysis of Variance (ANOVA) for each body site based on mITT data and/or per-protocol data. In the ANOVA model, the response is the log₁₀ reduction and the predictor is the treatment as a fixed effect. The average difference in log reduction between treatments at 10 minutes post-treatment time point will be estimated. However, all conclusions for the average treatment effect will be based on the primary analysis only.

An example for results of comparisons above can be found in Tables 9.

Table 9: Example: Log reduction comparisons for Groin

Comparison	N Pairs	Difference	Conf Int
IP Baseline-IP 10 min vs. VC Baseline-VC 10 min	24	0.13	-0.44, 0.70
IP Baseline-IP 10 min vs. SC Baseline-SC 10 min	24	0.11	-0.65, 0.87

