7.4.3.2 Product Expression Volumes/Weight

An analysis of variance (ANOVA) of the applied volumes/weight will be performed separately for each body site based on mITT data and/or per-protocol data. In the model, there will be a random subject effect, a fixed body side (left or right) effect, a fixed treatment effect and the interaction between fixed effects. ANOVA table will be checked to see whether the treatment has a significant effect on product expression volumes as well as the interaction. If a significant difference is found, subgroup comparisons with Tukey's method will be made to determine which pair of comparisons shows significant difference.

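### The primary regression treats the two products on each subject as independent readings, so the interval tested against 1.2 log10 ignores the bilateral design

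*SAP*

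**What the plan says.** Protocol 7.4.1.1 sets the design: "Each subject will receive two of the three possible treatments, one on the right side of the body and one on the left". SAP 3.3 gives the split: "12 subjects will receive treatments from both A and B, 12 subjects will receive treatments from both A and C", and 12 receive B and C. The primary analysis is the same in both documents. Protocol 17.3.1 states "A linear regression model will be used for primary analysis", and SAP 7.4.1 fits one such model per body site, in which "predictors are the treatment effect as a fixed effect and the pre-treatment" log10 count. Neither adds a subject effect, a within-subject covariance or a clustered standard error. Success requires the lower two-sided 95% bound to exceed 1.2 log10 for both controls at both body sites.

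Elsewhere the SAP does recognise the subject. For the baseline ANOVA, also in SAP 7.4.1: "In each model, there will be a random subject effect, a fixed treatment effect, a fixed body side effect". For product weight, SAP 7.4.3.2: "In the model, there will be a random subject effect, a fixed body side (left or right) effect, a fixed treatment effect". The exploratory log-reduction ANOVA in SAP 7.4.3.1 leaves it out again: the response is the log reduction "and the predictor is the treatment as a fixed effect". Protocol 8.0 says: "Each subject has four independent sampling sites: left and right sides for the abdomen and left and right sides for the groin".

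**The concern.** Two sides of one person, sampled on the same day, may well remain correlated after each side's own baseline is adjusted for. The ordinary regression standard error has no place for that correlation. It also pools one residual variance over three products, one of them an active antiseptic that may vary differently from the controls. Because all four lower bounds must clear 1.2, the standard error helps to decide the verdict.

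The study also exists to inform later efficacy studies (SAP 4). Those designs need a sound interval and an estimate of the within-subject correlation, and the plan does not commit to reporting one. The SAP gives no reason for modelling the subject in the baseline and weight analyses but not in the efficacy analyses. Example Tables 8 and 9 show 24 under N Pairs for IP vs. VC, although only 12 subjects receive both, so the tables do not settle whether pairing is meant to be used.

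**Working it through.** **Design count.** 36 subjects x 2 sides / 3 products = 24 readings per product per body site, which reproduces the plan's figure. Any two products share 12 subjects.

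**Inputs that must be assumed.** The documents give no planning SD, left-right correlation or true effect. Let s1 and s2 be the residual SDs of the test product and a control, and rho the left-right residual correlation after baseline adjustment.

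**Formulas (covariate omitted).**
- Actual variance of IP minus control: s1²/24 + s2²/24 - 2 x 12 x rho x s1 x s2/24² = (s1² + s2² - rho x s1 x s2)/24.
- Variance that the planned model reports: (mean of the three s²) x 2/24 = (mean s²)/12.
- With equal SD, reported SE / actual SE = 1/sqrt(1 - rho/2).
- Best possible variance with known covariance and SD 1: 1/[9/(1 - rho) + 3/(1 + rho)], which adds within-subject and between-subject information.

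**Equal SD 1.0.** The reported SE is sqrt(1/12) = 0.289 at every rho. For example, at rho 0.5 the actual SE is sqrt(1.5/24) = 0.250, and the best is sqrt(1/(18 + 2)) = 0.224. Coverage and pass rates come from simulating the regression with a baseline covariate (SD 0.53, slope 0.5, side correlation 0.5; 20,000 trials per scenario; Monte Carlo SE of coverage 0.15 points). CR2 is the small-sample cluster-robust standard error by subject. The pass columns give the chance that all four comparisons pass at a true effect of 2.0, with abdomen and groin assumed independent.

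| rho | Actual SE | Interval too wide by | Coverage of planned 95% CI | All four pass, planned | All four pass, CR2 |
|---|---|---|---|---|---|
| 0 | 0.289 | 0% | 94.9% | 43% | 40% |
| 0.1 | 0.281 | 3% | 95.4% | 43% | 43% |
| 0.3 | 0.266 | 8% | 96.8% | 47% | 52% |
| 0.5 | 0.250 | 15% | 97.7% | 50% | 61% |
| 0.7 | 0.233 | 24% | 98.5% | 53% | 72% |

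**Unequal SDs, IP 1.10 and both controls 0.72.** Mean s² = (1.21 + 0.5184 + 0.5184)/3 = 0.749, so the reported SE is sqrt(0.749/12) = 0.250. The actual variance is (1.7284 - 0.792 rho)/24, which gives SE 0.268, 0.262, 0.249 and 0.236 at rho 0, 0.1, 0.3 and 0.5. Setting 1.7284 - 0.792 rho = 2 x 0.749 gives a break-even at rho 0.29; below it the interval is too narrow. Simulated coverage at rho 0.1, 0.2, 0.3 and 0.5 is 93.6%, 94.5%, 94.8% and 96.2%. The one-sided error is 3.2%, 2.7%, 2.6% and 1.9%, against a nominal 2.5%.

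**SDs 1.10 / 1.09 / 0.72 for IP / VC / SC.** These are the 10-minute SDs in example Table 6, used only as an illustration. At rho 0.1, 0.3 and 0.5, IP vs. VC covers 93.1%, 94.4% and 95.8%, while IP vs. SC covers 96.5%, 97.4% and 98.0%. One pooled standard error can thus err in opposite directions within one verdict.

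**Cluster-robust alternative.** CR2 covers 94.8% to 95.9% in all 20 scenarios simulated. With incomplete pairs (42 subjects, 25% with one evaluable side, rho 0.5), the planned interval covers 97.2% and CR2 95.3%; all four comparisons pass in 49% and 59% of trials.

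**The case against.** The strongest reply is that the error is usually harmless to the claim. With similar variances and positive correlation the interval is too wide, so a false pass becomes less likely, and the study is expressly not powered. The size is unknown: only correlation left after baseline adjustment counts, and at rho 0.1 to 0.3 the excess width is 3% to 8%. The large figures need rho of 0.5 to 0.7. All of this stands, and it limits the weight of the point.

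The under-coverage has a different source. With SDs 1.10/0.72/0.72 it is worst at rho 0 (about 93.3%), and the correlation offsets it. That is right: the cause is one pooled variance over unequal products. It still means the planned interval cannot be defended as always conservative, and the same change of standard error cures both problems.

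The supporting evidence is also softer than the model text. Table 6 is a placeholder: its product B means give 5.78 - 3.27 = 2.51, against 2.83 in Table 7. Its SDs are raw rather than residual, and assigning codes A and B to products is arbitrary. The Protocol 8.0 sentence may only describe how readings are counted, and N Pairs may mean baseline and post-treatment pairs. None of this touches the omission itself, which rests on the wording of the primary model.

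Finally, the plan follows FDA letters of January 2017, whose content is not reproduced, and they may prescribe the regression. The remedy below therefore keeps it.

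**Conclusion.** The point holds and should be fixed. The efficacy models leave out the subject although the design pairs products within subjects and the same SAP models the subject elsewhere. No other section supplies a within-subject covariance for them. The estimate is not biased by this.

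Under equal residual SDs and rho between 0.1 and 0.7, the interval compared with 1.2 is 3% to 24% too wide, and precision that the bilateral design paid for is lost. At rho 0 with equal SDs nothing is lost. Under unequal SDs the interval can be about right or too narrow. Every size given rests on assumed SDs, correlations and true effect with 12/12/12 complete pairs, except where incomplete pairs are stated. The joint pass rates also assume independent body sites.

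**What to change.** Before unblinding, amend SAP 7.4.1:

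- Keep the regression, its estimate and the rule that the lower two-sided 95% bound must exceed 1.2. Replace the model-based standard error with CR2 clustered on subject, with Satterthwaite degrees of freedom, for the model with and without the interaction. This stays valid with unequal variances, and with the incomplete pairs that arise because SAP 6.1 judges inclusion per body area.
- Pre-specify a supportive mixed model with the same fixed effects, a random subject effect, treatment-specific residual variances and Kenward-Roger degrees of freedom. Report its within-subject correlation for later designs. It is more precise at high rho (all four pass in 75% of trials at rho 0.5, against 61% with CR2). It can under-cover slightly, at 93.5% to 94.4%, when IP-control rho is 0.1 and control-control rho is 0.7, so it should not decide the verdict alone.
- Treat the log-reduction ANOVA in SAP 7.4.3.1 the same way.
- Optionally add a body-side term, define N Pairs, and reword the independence sentence in Protocol 8.0.

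The SAP changes cost wording and a few lines of R, with no new data or subjects. Protocol 17.0 leaves analysis details to the SAP, and the Protocol 17.3.1 description stays true. Making the mixed model primary would need a protocol amendment with IRB/EC approval (Protocol 19.4). The price of CR2 is an interval about 2% wider at rho 0 with equal SDs (half-width 0.588 against 0.578). At rho 0.1 with SDs 1.10/0.72/0.72, where the planned interval is too narrow, it is about 7% wider.
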